[Part 3 of 3 of the document. The other parts are not shown.]

- To demonstrate weight loss efficacy by achieving a greater proportion (%) of subjects with at least a 5% reduction in BMI after an initial 12 weeks of treatment with Belviq XR 20 mg administered QD compared to placebo
- To demonstrate that achieving at least a 5% reduction in BMI after an initial 12 weeks of treatment with Belviq XR 20 mg administered QD is predictive of sustained change in BMI during 52 weeks of treatment with Belviq XR 20 mg administered QD
- To demonstrate the efficacy of treatment with Belviq XR 20 mg QD by assessing:
 - Other weight loss effects (eg, proportion [%] of subjects achieving at least a 10% BMI reduction, change in waist circumference) at the end of 52 weeks of treatment
 - Effects on glycemia, insulin levels, and Homeostatic Model Assessment of Insulin Resistance (HOMA-IR; $\text{glucose [mg/dL]} \times \text{insulin [mU/L]}/405$) during 52 weeks of treatment
 - Changes in cardiovascular risk factors associated with obesity (eg, hypertension, dyslipidemia) including fasting lipid changes (total cholesterol, triglycerides, high density lipoprotein [HDL], and low density lipoprotein [LDL]) during 52 weeks of treatment
- To assess the safety of Belviq XR, including the effects on cognitive function by Wide Range Assessment of Memory and Learning-2 (WRAML-2), on depression by the Patient Health Questionnaire (PHQ-9), on signal of suicidal ideation or behavior with the Columbia-Suicide Severity Rating Scale (C-SSRS), on growth measured by CDC growth chart, on sexual maturation (pubescence) measured by Tanner Staging scores, and on other growth and development parameters by measuring sex hormones, thyroid function, valvular function, pulmonary arterial pressure, adrenal function, bone age, and biochemical markers of bone health assessments
- To assess the pharmacokinetic (PK) of lorcaserin using population PK modeling

- To assess relationships between plasma exposure to lorcaserin and pharmacodynamic (PD) parameters including but not limited to reduction from baseline in BMI and probability of achieving at least a 5% and at least a 10% reduction in BMI from baseline at Week 52 using population PK/ PD modeling

9 INVESTIGATIONAL PLAN

9.1 Overall Study Design and Plan

This is a multicenter, randomized, double-blind, placebo-controlled, parallel-group study in obese adolescents ages 12 to 17 years. Approximately 360 subjects will be randomized in a 1:1 ratio to Belviq XR 20 mg QD (180 subjects) and placebo (180 subjects). Subjects will be stratified by sex. Subjects will receive Belviq XR 20 mg or placebo QD in a 1:1 ratio for up to 52 weeks. Throughout the duration of the study, subjects will be encouraged to adhere to a lifestyle modification program that includes a standardized, age-appropriate diet and exercise counseling (see [Appendix 2](#)).

The study will consist of 2 phases: Prerandomization and Randomization. The Prerandomization Phase will last up to 30 days and consists of 1 visit during which subjects will be screened for eligibility. The Randomization Phase consists of a Treatment Period and a Follow-Up Period. The Treatment Period will last for a maximum of 52 weeks, with visits at Weeks 1, 5, 8, 12, 20, 28, 36, 44, and 52; the Follow-Up Period will extend from the End of Treatment (EOT) visit to the End of Study (EOS) visit.

Subjects who screen fail can be re-screened only once after 60 days. All subjects will continue in the study until the 52-week evaluation is completed. Subjects who discontinue treatment prematurely will be followed up until study completion.

9.1.1 Prerandomization/Pretreatment Phase

Screening will occur during the Prerandomization Phase at Visit 1

9.1.1.1 Screening Period

The purpose of the Screening Period is to obtain the informed consent and assent and to establish protocol eligibility. Procedures to be followed when obtaining informed consent are detailed in [Section 5.3](#). Careful initial screening is important in the recruitment of families who both fully understand the requirements of this 1 year, randomized, controlled trial and are truly interested in participation. Interested caregivers and adolescents will be screened by phone to assess preliminary entry criteria. Candidates will be given a brief description of the program and general study requirements, with an adolescent and a caregiver who is willing to participate. If preliminary entry criteria are met, adolescents and their caregivers will be invited to an initial in-clinic meeting to further discuss the study. A complete description of the study including assessments, the number of visits, the lifestyle program, the fact that the adolescent would be taking either the study drug or a placebo, the duration of the study, and the necessity of having an adolescent wishing to participate as well as a participating caregiver will be described. Consent and assent will be obtained and copies of the signed forms will be provided to families. The importance of the study and its scientific merit will be discussed. Ineligible adolescents will be referred to local weight management resources. Screening period assessments and timing thereof are shown in [Section 9.5.2](#).

9.1.2 Randomization/Treatment Phase

The Randomization Phase will consist of 2 periods: the Treatment Period and the Follow-Up Period. The Treatment Period assessments and timing thereof are shown in [Section 9.5.2](#).

9.1.3 Extension Phase

Not applicable

9.2 Discussion of Study Design, Including Choice of Control Groups

The proposed dose and dosing frequency of Belviq XR in this study is 20 mg QD. The PK parameters of a single 10-mg dose of Belviq were evaluated in healthy, adolescent obese subjects in Study APD356-025. Overall, the PK parameters of Belviq and its main metabolites, M1 and M5, were similar to those in adults. Following a single, oral administration of Belviq 10 mg to a total of 8 healthy adolescent (ages 12 to 17 years old) obese subjects, the mean maximum concentration observed and the area under the concentration-time curve from time zero to infinity ($AUC_{(0-inf)}$) were 36.5 ng/mL and 464 hr \times ng/mL, respectively. The mean Belviq terminal phase half-life was 9.70 hours, similar to that observed in adults, thus supporting a similar dosing frequency (QD) in adolescent subjects.

Additionally, a single dose PK study in 8 healthy obese pediatric subjects ages 6 to 11 years of age was performed. The PK analysis after a single 10-mg dose of lorcaserin revealed that the lorcaserin $AUC_{(0-inf)}$ values tended to increase with decreasing body weight and age. However, the body weight normalized $AUC_{(0-inf)}$ values were similar across the age groups, therefore the data indicated no effect of age on the lorcaserin PK. Integrated assessment of the PK versus body weight relationship, pooling the data from pediatric and adult subjects from previous studies, suggested that the lorcaserin area under the curve values for subjects with body weight of at least 60 kg overlapped with the area under the curve values from adolescents and adults. Therefore, no dose adjustment relative to adults and adolescents is deemed necessary for pediatric or adolescent subjects with a body weight of at least 60 kg.

Based on CDC growth charts, the likelihood of subjects who are older than 12 years of age having a body weight of less than 60 kg is very low; therefore, the current study as designed to enroll subjects between 12 to 17 years of age with body weight at least 60 kg, will cover majority of the population of interest. The targeted study population comprises 360 obese adolescents 12 to 17 years of age, with a body weight at least 60 kg.

Obese adolescents will be identified using gender- and age-specific BMI measurement. Obesity in adolescents is defined by US Expert committee recommendations as BMI in or above the 95th percentile ([Barlow, 2007](#)).

Randomization will be used in this study to avoid bias in the assignment of subjects to treatment, to increase the likelihood that known and unknown subject attributes (eg, demographics, baseline characteristics) are balanced across treatment groups, and to ensure the validity of statistical comparisons across treatment groups. Blinding to treatment will be used to reduce potential bias during data collection and evaluation of endpoints.

9.3 Selection of Study Population

Approximately 700 subjects will be screened to ensure that 360 subjects will be randomized.

Subjects who do not meet all inclusion criteria or do meet any exclusion criteria will not be eligible to receive study drug. Subjects who screen fail can be re-screened only once after 60 days.

9.3.1 Inclusion Criteria

Subjects must meet all of the following criteria to be included in this study:

1. Healthy male or female adolescents, ages 12 to 17 years old at Screening, with a BMI that is greater than or equal to the United States (US)-weighted mean of the 95th percentile based on age and sex with a body weight greater than 60 kg
2. Subjects and their families are not planning to move away from the area for the duration of the study
3. Subjects able and willing to comply with all aspects of the study, including a standardized, reduced-calorie diet and an age-appropriate, increased physical activity program
4. Subjects considered in stable health in the opinion of the investigator
5. Caregivers or guardians meet the following requirements:
 - a. Able and willing to support and supervise study participation in the opinion of the investigator, including consideration of any existing physical, medical, or mental condition that prevents compliance with the protocol
 - b. Able and willing to personally comply with and execute all aspects of the study requirements for the caregivers or guardians

9.3.2 Exclusion Criteria

Subjects who meet any of the following criteria will be excluded from this study:

1. Clinically significant new illness within 1 month before randomization that may affect the subject's ability to fulfill the study requirements or significantly confound the assessments
2. Subjects who cannot swallow investigational products
3. Any of the following findings on screening echocardiography:
 - Aortic regurgitation mild or greater

- Mitral regurgitation moderate or greater
 - Mitral or aortic valve stenosis greater than mild (ie, aortic stenosis [AS]: jet >3.0 m/s, mean gradient >25 mm Hg, and aortic valve area [AVA] <1.5 cm²; MS: mean gradient >5 mm Hg and mitral valve area [MVA] <1.5 cm²)
 - Systolic pulmonary artery pressure (SPAP) >40 mm Hg (and/or tricuspid regurgitation (TR) jet velocity >2.9 m/s)
 - In cases where an actual SPAP value is not measurable due to lack of adequate TR jet, the pulmonary flow acceleration time measured at the right ventricular outflow tract (RVOTAT), will be used to assess eligibility. Patients with a RVOTAT ≤100 msec will be excluded, suggesting an elevated mean SPAP; eligibility for the those patients with RVOTAT between 100 and 120 msec will be determined based on combined assessment of the TR jet, septal motion and right ventricular size.
 - Left ventricular ejection fraction <45%
 - Intracardiac mass, tumor or thrombus
 - Evidence of congenital heart disease
 - Clinically significant pericardial effusion (eg, moderate or larger or with hemodynamic compromise)
4. Significant renal or hepatic disease as evidenced by a serum creatinine greater than 1.5×upper limit of normal (ULN), serum transaminases greater than 3×ULN, or total bilirubin greater than 1.5×ULN in absence of Gilbert’s syndrome
 5. Any history of anorexia or bulimia within 2 years before Screening, Attention Deficit Hyperactivity Disorder, any Diagnostic and Statistical Manual of Mental Disorders, 5th Edition depressive disorder, suicidal ideation or behavior, bipolar disorder, or schizophrenia
 6. Known secondary causes (chromosomal, endocrine, or metabolic) for obesity (eg Prader-Willi syndrome, Bardet Biedl syndrome, Down’s Syndrome, untreated hypothyroidism, Cushing’s syndrome, daily systemic corticosteroid exposure for longer than 30 days, history of significant exposure to corticosteroids for chronic illness during the past year, and known genetic causes of obesity)
 7. Use of other products intended for weight loss including prescription drugs, over-the-counter (OTC) drugs, and herbal preparations within 1 month before Screening
 8. Use of any of the following medications:
 - a) Serotonergic drugs within 7 days (or 5 half-lives, whichever is longer) or monoamine oxidase inhibitors (MAOIs) within 30 days before Randomization, including:
 - selective serotonin reuptake inhibitors (SSRIs)
 - serotonin norepinephrine reuptake inhibitors (SNRIs)
 - tricyclic antidepressants (TCAs)

- bupropion
 - triptans
 - St. John's Wort
 - tryptophan
 - linezolid
 - dextromethorphan in any form (eg, OTC cold medicines)
 - lithium
 - tramadol
 - antipsychotics or other dopamine antagonists
- b) Others
- antiseizure medications including valproic acid, zonisamide, topiramate and lamotrigine
 - oral steroids (topical and inhaled steroids are acceptable)
 - stimulant medications (Ritalin, Concerta, Biphedamine and Dexedrine)
 - benzodiazepines
9. Use of drugs known to increase the risk for cardiac valvulopathy within 6 months before Screening, including but not limited to pergolide, ergotamine, methysergide, and cabergoline
 10. History or evidence of clinically significant disease (eg, malignancy; cardiac, respiratory, gastrointestinal, renal, or psychiatric disease) other than prediabetes (impaired fasting glucose or impaired glucose tolerance), Type 2 diabetes treated with oral anti-diabetic agents (excluding sulfonylurea) or non-insulin injectable antidiabetic agents, obstructive sleep apnea, dyslipidemia, and nonalcoholic fatty liver disease
 11. Use of Belviq XR within 6 months before Screening or hypersensitivity to Belviq XR or any of the excipients
 12. Significant change in diet or level of physical activity within 1 month before dosing or change in weight of more than 5 kg within 3 months before Screening
 13. Any use of a of very-low-calorie (<1000 calories/day) weight loss diet within 6 months before Screening
 14. History of alcohol or drug dependence or abuse
 15. Recreational drug use within 2 years before Screening
 16. Known to be human immunodeficiency virus positive
 17. Active viral hepatitis (B or C) as demonstrated by positive serology
 18. Malignancy within 5 years before Screening
 19. Unable to attend scheduled visits (eg, lack of transportation) or lack of a caregiver or guardian to supervise study participation

20. Special needs subjects who are unable to comprehend study-related instructions (eg, mild to profound mental retardation [IQ <70], moderate to severe cognitive developmental delay, pervasive development disorders, autism)
21. Ongoing epilepsy or other seizure disorder, or use of medications for a seizure disorder within 6 months of screening or any time between screening and randomization
22. Subjects with a BP in the 95th percentile or greater for age, sex, and height on 2 separate readings recorded on 2 separate days. Those subjects who had uncontrolled hypertension at Screening can be rescreened more than 1 month after initiation or adjustment of antihypertensive therapy 1 time.
23. Currently enrolled in another clinical study or has used any investigational drug or device within 30 days before providing informed consent
24. Planned bariatric surgery during the study
25. Not suitable to participate in the study in the opinion of the investigator, including consideration of any existing physical, medical, or mental condition that prevents compliance with the protocol
26. Female subjects who are breastfeeding or pregnant at Screening or Baseline (as documented by a positive β -human chorionic gonadotropin test). A separate Baseline assessment is required if a negative screening pregnancy test was obtained more than 72 hours before the first dose of study drug.
27. Female subjects of childbearing potential who:
 - a. Had unprotected sexual intercourse within 30 days before study entry and who do not agree to use a highly effective method of contraception (eg, total abstinence, an intrauterine device, a double-barrier method [such as condom plus diaphragm with spermicide], a contraceptive implant, an oral contraceptive, or have a vasectomized partner with confirmed azoospermia) throughout the entire study period and for 28 days after study drug discontinuation
 - b. Are currently abstinent, and do not agree to use a double-barrier method (as described above) or refrain from sexual activity during the study period and for 28 days after study drug discontinuation
 - c. Are using hormonal contraceptives but are not on a stable dose of the same hormonal contraceptive product for at least 4 weeks before dosing and who do not agree to use the same contraceptive during the study and for 28 days after study drug discontinuation

(NOTE: All female subjects will be considered to be of childbearing potential unless they have been sterilized surgically [ie, bilateral tubal ligation, total hysterectomy, or bilateral oophorectomy, all with surgery at least 1 month before dosing]).

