9.5.4.2 Reporting of Pregnancy and Exposure to Study Drug through Breastfeeding

Any pregnancy in which the estimated date of conception is either before the last visit or within 28 days of last study treatment or any exposure to study drug through breastfeeding during study treatment or within 28 days of last study treatment must be reported.

If an adverse outcome of a pregnancy is suspected to be related to study drug exposure, this should be reported regardless of the length of time that has passed since the exposure to study treatment.

A congenital anomaly, death during perinatal period, an induced abortion, or a spontaneous abortion are considered to be an SAE and should be reported in the same time frame and in the same format as all other SAEs (see [Section 9.5.4.1](#)).

Pregnancies or exposure to study drug through breastfeeding must be reported by fax or email as soon as possible but no later than 1 business day from the date the investigator becomes aware of the pregnancy. The contact information for the reporting of pregnancies and exposure to study drug through breastfeeding is provided in the Investigator Study File. The Pregnancy Report Form must be used for reporting. All pregnancies must be followed to outcome. The outcome of the pregnancy must be reported as soon as possible but no later than 1 business day from the date the investigator becomes aware of the outcome.

A subject who becomes pregnant must be withdrawn from the study.

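### Exclusion criterion 27 leaves two groups of females of childbearing potential outside its contraception commitment

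*Protocol*

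**What the plan says.** Protocol section 9.3.2 opens its list with "Subjects who meet any of the following criteria will be excluded from this study", so meeting any one criterion is enough to exclude. Criterion 27, in the version for ages 12 to 17, concerns females of childbearing potential. The note beneath it makes that group wide: "All female subjects will be considered to be of childbearing potential unless they have been sterilized surgically".

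The criterion has three limbs, read here as alternatives:

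- Limb a: "Had unprotected sexual intercourse within 30 days before study entry and who do not agree to use a highly effective method of contraception", for the study period and 28 days after study drug is stopped.
- Limb b: "Are currently abstinent, and do not agree to use a double-barrier method (as described above) or refrain from sexual activity during the study period", with the same 28-day extension.
- Limb c: "Are using hormonal contraceptives but are not on a stable dose of the same hormonal contraceptive product for at least 4 weeks before dosing", followed directly by "and who do not agree to use the same contraceptive during the study and for 28 days after study drug discontinuation".

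The inclusion criteria in section 9.3.1 contain no contraception requirement. Criterion 26 excludes subjects who are pregnant or breastfeeding at Screening or Baseline, and requires a separate Baseline test if the negative screening test was more than 72 hours before the first dose. Table 2 schedules a urine pregnancy test at every planned visit from Screening to Week 56. Section 9.5.4.2 adds: "A subject who becomes pregnant must be withdrawn from the study".

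**The concern.** The purpose of such a criterion is to obtain an undertaking on contraception before study drug is given. In criterion 27 the undertaking is never a requirement by itself. It appears only as the second half of a condition whose first half is a particular status, so a subject without one of those statuses is never asked for it.

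The result is also uneven. A subject who is abstinent must commit under limb b, while some subjects who are sexually active need not. Under limb c, having been stable for 4 weeks takes a hormonal user out of the limb altogether, so stability releases her from agreeing to continue.

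At stake is unintended fetal exposure to study drug, and uneven practice between sites: a site that applies the text exactly can enrol these subjects with no commitment, while a site that applies what it takes to be the intent will not.

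**Working it through.** No figure in the plan is at issue, so the check is one of logic.

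**Inputs**, all from criterion 27: U = unprotected intercourse within 30 days before entry; A = currently abstinent; H = hormonal user; S = stable on the same product for at least 4 weeks; G = agrees to the commitment named in the limb concerned.

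**Rule as written:**

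excluded = (U and not G) or (A and not G) or (H and not S and not G)

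Every term contains *not G*, so a subject who agrees is never excluded by criterion 27. The informative column is therefore what happens to a subject who refuses.

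| Contraceptive history | Limb met on refusal | Excluded if she refuses |
|---|---|---|
| Unprotected intercourse within 30 days, no hormones | a | Yes |
| Abstinent | b | Yes |
| Hormonal, under 4 weeks, no unprotected intercourse | c | Yes |
| Hormonal, under 4 weeks, with unprotected intercourse | a and c | Yes |
| Hormonal, stable 4 weeks, no unprotected intercourse | none | **No** |
| Sexually active, single barrier only | none | **No** |

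Six histories by two answers give 12 profiles. As written, 0 of the 6 who agree and 4 of the 6 who refuse are excluded: 4 of 12. If refusal excluded whatever the history, 6 of 12 would be. The difference is 6 − 4 = 2 profiles, the last two rows. These count logical cases and say nothing about how many subjects fall in each.

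**Stable hormonal user.** Limb c needs H, not S and not G together. With S true it cannot be met, whatever she answers. She is still caught if limb a or b applies to her separately, so the gap concerns a stable user who is not abstinent and has had no recent unprotected intercourse.

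**Four-week condition.** With G true limb c cannot be met either, so the stability condition excludes nobody who agrees to continue.

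**Single-barrier user.** With U, A and H all false, no term can be true. This gap is one of coverage: no limb describes her, and the word joining the conditions plays no part in it. It depends on condom use not counting as unprotected.

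**Other provisions.** Criterion 26 and the Table 2 tests establish whether a subject is pregnant. Neither asks for an undertaking. Criterion 25 and the investigator's discretion to withdraw a subject (section 9.3.3) are general judgement.

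**The case against.** The strongest reply is that most of criterion 27 works. Subjects with recent unprotected intercourse, abstinent subjects and new hormonal users are all excluded if they refuse. That stands. A reader might infer that the contraception requirements do not bind at all; the table shows that they bind in four of the six histories.

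A second reply is that limb a is deliberate: recent exposure is acceptable if the subject commits to contraception and the criterion 26 test is negative. Nothing in the protocol says that recent intercourse was meant to exclude by itself. The first version bound in the file extended the commitment with *or* for 30 days; later text has *and* for 28 days. The sponsor thus edited these limbs and kept the pairing of status with refusal. That is an inference about intent, but it counts against calling limb a an error. It follows that replacing *and* with *or* is not supported: it would create a new eligibility rule, barring for 30 days a subject who agrees and tests negative.

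A third reply is that the single-barrier gap rests on an undefined word. This stands as a condition on that half of the point. It does not touch the stable hormonal user.

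A reader might also infer a loss of efficacy data, since pregnancy means withdrawal, and a missing Week 52 assessment counts as failure in the key secondary analysis (section 9.7.1.6). The documents do not support giving that weight: no pregnancy number is stated, missing primary values are imputed, and the sample size already allows 40% dropout (section 9.7.2).

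Finally, only part of the protocol file is at hand and consent pages were removed, so a commitment obtained elsewhere cannot be ruled out. It would not make criterion 27 read correctly.

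**Conclusion.** The point holds in limited form. Criterion 27 does not apply its contraception commitment to every female of childbearing potential. Followed as written, it lets two groups enter without one: stable hormonal users who decline to continue, and sexually active, non-hormonal subjects whose recent intercourse was protected. In addition, the 4-week condition has no effect on anyone who agrees to continue.

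The conclusion assumes that the three limbs are alternatives, that the stable user is neither abstinent nor recently exposed without protection, and, for the second group only, that a single barrier is not unprotected intercourse. The number of subjects or pregnancies affected cannot be derived from the document. The same pairing appears in the earlier versions bound in the file, where the criterion is numbered 28, so it is not a conversion fault. The wording should be corrected, because applying it exactly gives a result at odds with its evident purpose.

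**What to change.** Reconcile limbs a to c so that any female of childbearing potential who refuses the commitment the criterion already states, for the study and 28 days after study drug is stopped, is excluded whatever her recent practice. Because the limbs name different commitments, the text must also say which one applies to a stable hormonal user and to a sexually active, non-hormonal subject. Define unprotected.

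Separately, the sponsor should state whether the 30-day condition in limb a and the 4-week condition in limb c are meant to exclude on their own. Which methods and time windows are right is for the sponsor to decide.

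The cost is amendment wording and possibly a few more screen failures. No new procedure or visit is needed.
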